3.7.6 End of Trial

The end of trial date is defined as the last date of contact or the date of final contact attempt from the post-treatment follow-up case report form (CRF) page for the last subject completing or withdrawing from the trial.

3.8 Stopping Rules, Withdrawal Criteria, and Procedures

3.8.1 Entire Trial or Treatment Arms

If the sponsor terminates or suspends the trial for any reason, prompt notification will be given to the heads of trial sites and regulatory authorities in accordance with regulatory requirements.

Confidential - Proprietary Information

3.8.2 Individual Site

Individual trial site participation may be discontinued by the sponsor, the investigator, or the IRB if judged to be necessary for medical, safety, regulatory, ethical or other reasons consistent with applicable laws, regulations, and GCP. The head of the trial site will notify the sponsor promptly if the trial is terminated by the investigator or the IRB at the site.

3.8.3 Individual Subject Discontinuation

3.8.3.1 Treatment Discontinuation

In the event of any of 1) through 10) below, IMP administration in the subject will be stopped followed by the withdrawal examination specified in Section 3.7.1 Schedule of Assessments. The investigator or subinvestigator will record the event in detail in source documents and CRF together with the date and reason for discontinuation.

- 1) Subject's request for withdrawal
- 2) Discovery that the subject does not meet the inclusion criteria (including those for enrollment in the treatment period) or falls under any of the exclusion criteria after the start of the treatment period
- 3) Occurrence of an AE(s) that makes continued IMP administration difficult
- 4) A clinical laboratory value (AST or ALT) is obtained that equals or exceeds 3 times the upper limit of normal (ULN)
- 5) It is found that the serum sodium concentration determined at the trial site or central laboratory has increased to 12 mEq/L or higher from the predose value within 24 hours after the start of IMP administration
- 6) It is found that the serum sodium concentration determined at the trial site or central laboratory has increased to 155 mEq/L or higher during the treatment period
- 7) Use of prohibited concomitant drugs
- 8) Noncompliance with rule 1) in the restrictions for concomitant drugs
- 9) Confirmed or suspected pregnancy after the start of the treatment period
- 10) Deviation from the protocol becomes inevitable or the investigator or subinvestigator decides that the subject needs to be withdrawn from the trial for any other reason

After randomization, a subject may stop treatment permanently for a variety of reasons. Treatment discontinuations may be initiated by a subject who is not satisfied with treatment or may become medically necessary due to AEs, required treatment with a disallowed medication or therapy, or other issues, as determined by the investigator or

subinvestigator. However, each investigator or subinvestigator must comprehensively review the circumstances and offer the subject options for continued treatment to the degree possible as described in Section 3.8.3.4.

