Subjects are registered and randomized at screening and on Day 1, respectively, in the IWRS. Only the subjects who meet all the inclusion criteria (including the criteria specified in "Table 3.4.3-1 Criteria for Enrollment in the Treatment Period (Inclusion Criteria of Run-in Period)") and do not fall under any of the exclusion criteria are assigned to IMP administration. Randomization normally takes place on Day 1 (or Day -1 if justified. Each subject's fulfillment of inclusion criterion 8 will be verified on Day 1). Completion of the initial administration (Day 1), completion of blood sampling

^aSubject enrollment/randomization:

for plasma drug concentration measurement up to 24 hours after start of IMP administration on Day 1 (Day 2), and trial completion/discontinuation (end-of-trial/withdrawal) will be recorded in the IWRS.

^bTiming of blood sampling on Day 1 for measurement of serum sodium/potassium concentration:

Before IMP administration (before breakfast), between 4 and 6 hours after start of IMP administration, and between 8 and 12 hours after start of IMP administration. Measurement of serum sodium concentration during the treatment period takes place at the trial site in addition to at the central laboratory.

^cBiomarkers:

Plasma AVP concentration, plasma BNP concentration, plasma renin activity, serum NT-proBNP concentration, serum troponin concentration will be measured.

^dVital signs: Blood pressure, pulse rate, and body temperature will be measured.

^e12-lead ECG: Between 1 and 2 hours after start of IMP administration on Day 1 and Day 3. Subsequently when possible.

^fPregnancy test: Applicable to only female subjects of childbearing potential.

^gCongestive symptoms: Lower limb edema, other edema, jugular venous distension, pulmonary rales, third cardiac sound, hepatomegaly will be assessed.

hChest X-ray: Cardiothoracic ratio and pulmonary congestion will be assessed.

If the subject underwent chest X-ray at examination before participation in the trial, cardiothoracic ratio and pulmonary congestion may be assessed using the radiograph (must be taken within 14 days before consent) instead of obtaining a new one at the screening examination.

ⁱDNA storage: Blood will be collected before IMP administration on Day 1.

If blood cannot be collected at the above time point, collection may take place at any subsequent time point during the trial.

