3.7.1 Schedule of Assessments

3.7.1.1 Screening

After obtaining informed consent, the investigator or subinvestigator will assign a subject identifier to each subject according to Section 3.3.2 Subject Selection and Numbering. The date of consent and subject identifier will be recorded in source documents and CRF. The subject will then be registered in the IWRS. The IWRS will be used to monitor subject registration, etc. The use of the system will be described in a separate procedure.

After acquisition of informed consent, subjects will undergo the following screening (examinations/tests) between 7 days and 4 days before administration (Day –7 to Day –4) for eligibility assessment. The result of eligibility assessment will be recorded in source documents and CRF.

[Tests/Examinations]

Subject demographics [birth date, sex, height, nationality, race, ethnicity, underlying disease, heart failure subtype, presence/absence and type of arrhythmia, presence/absence of pacemaker, presence/absence of ICD, complications, and medical history], serum sodium concentration, serum potassium concentration, clinical laboratory tests, physical examination, vital signs (blood pressure, pulse rate, and body temperature), body weight, congestive symptoms, chest X-ray^{Note} (cardiothoracic ratio and pulmonary congestion), confirmation of use of concomitant medications and therapies, urine pregnancy test (only in female subjects of childbearing potential)

Note) If the subject underwent chest X-ray at examination before participation in the trial, cardiothoracic ratio and pulmonary congestion may be assessed using the radiograph (must be taken within 14 days before consent) instead of obtaining a new one at the screening examination.

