3.7.1.4 Treatment Period (Day 1)

(1) Before IMP Administration (Before Breakfast)

- Plasma drug concentration (within 2 hours before IMP administration)
- Serum sodium concentration, serum potassium concentration, serum osmolality, and biomarkers
- Clinical laboratory tests and vital signs
- Body weight
- Blood sampling for DNA storage (The subject may or may not agree to DNA storage. The subject's consent to DNA storage will be obtained before blood sampling.)

(2) After Tests/Blood Sampling and After Breakfast

The subject will be asked to void his/her bladder immediately after breakfast to start pooling of urine and measurement of fluid intake for the following measurements:

- Daily urine volume, daily fluid intake, and daily fluid balance
- Daily urine sodium excretion and daily urine potassium excretion
- Urine osmolality

(3) IMP Administration

The investigator or subinvestigator will administer the IMP to the subject after verifying that the subject meets the inclusion criteria and does not fall under any of the exclusion criteria. The investigator or subinvestigator subsequently will record IMP administration in the IWRS.

(4) Administration of Diuretics

(5) Tests and Assessments

The investigator or subinvestigator will perform the tests described below.

Table 3.7.1.4-1 Tests on Day 1, Their Scheduled Time Points, and Blood Sampling Time Points After IMP Administration							
Sampi							
Item	Time Point	Time Window					
Plasma drug concentration	1 hour after start of IMP	Within 5 minutes after end					
	administration	of IMP administration					
	1.5 hours after start of IMP	Specified time point ± 5					
	administration	minutes					
	2 hours after start of IMP	Specified time point ± 5					
	administration	minutes					
	4 hours after start of IMP	Specified time point ± 20					
	administration	minutes					
	6 hours after start of IMP	Specified time point ± 30					
	administration	minutes					
	12 hours after start of IMP	Specified time point ± 1 hour					
	administration						
Serum sodium concentration,	4 to 6 hours after start of IMP						
serum potassium concentration	administration						
	8 to 12 hours after start of IMP						
	administration						
12-lead ECG	1 to 2 hours after start of IMP						
	administration						
Physical examination	When appropriate on Day 1						
Congestive symptoms	When appropriate on Day 1						
Confirmation of use of	When appropriate on Day 1						
concomitant drugs and therapies	-						

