3.7.1.5 Treatment Period (Day 2)

(1) Before IMP Administration (Before Breakfast)

- Plasma drug concentration (24 hours after start of IMP administration on Day 1)
- Serum sodium concentration and serum potassium concentration
- Vital signs
- Body weight

(2) After Tests/Blood Sampling and After Breakfast

The subject will be asked to void his/her bladder immediately after breakfast to start pooling of urine and measurement of fluid intake for the following measurements:

• Daily urine volume, daily fluid intake, and daily fluid balance

- Daily urine sodium excretion and daily urine potassium excretion
- Urine osmolality
- (3) IMP Administration
- (4) Administration of Diuretics
- (5) When Appropriate on Day 2
 - Physical examination
 - Congestive symptoms
 - Confirmation of use of concomitant drugs and therapies
 - Treatment compliance
 - AEs

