3.7.1.9 Post-treatment Follow-up Period (7 to 10 days after final administration)

The investigator or subinvestigator will perform the following tests or examinations between 7 and 10 days after final IMP administration. The tests/examinations may be performed on an outpatient basis if the subject has been discharged.

- Serum sodium concentration and serum potassium concentration
- Clinical laboratory tests, physical examination, and vital signs
- Body weight and congestive symptoms
- Urine pregnancy test (only in female subjects of childbearing potential)
- Confirmation of use of concomitant drugs and therapies
- AEs

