3.7.4.2 Clinical Laboratory Assessments

The patient will undergo venous blood withdrawal and urine collection for the clinical laboratory tests specified in Table 3.7.4.2-1 at specified time points. The date and time of blood sampling and the date of urine collection will be recorded in source documents. The samples will be sent to the contract laboratory for central testing.

To ensure subject safety and to facilitate close monitoring of serum sodium concentration by the investigator or subinvestigator, serum sodium concentration will be determined at the trial site during the treatment period separately from the measurement at the contract laboratory. Whether blood for measurement of serum sodium concentration is collected and, if collected, the date and time of blood sampling and the result of measurement will be recorded in the source documents and CRF.

The contract laboratory will perform the measurements for the parameters listed in the table below according to their established procedure and report the results to the sponsor and the investigator or subinvestigator. Whether blood and urine have been collected as well as the date and time of blood sampling and the date of urine collection (if collected) will be recorded in the CRF. The electronic file documenting the test results will be

delivered from the contract laboratory to the sponsor and kept as source data. Transcription of the results into the CRF is unnecessary.

Table 3.7.4.2-1 Clinical Laboratory Assessments		
Hematology:	Serum Chemistry:	
Red Blood Cell count	Protein, total	
Hemoglobin	Albumin	
Hematocrit	Bilirubin, total	
White Blood Cell count with differential	AST (GOT)	
(neutrophil, eosinophil, basophil, monocyte,	ALT (GPT)	
lymphocyte)	Alkaline phosphatase (ALP)	
Platelet count	γ-Glutamyl transferase (γ-GTP)	
Urinalysis (qualitative):	Lactic dehydrogenase (LDH)	
pH	Creatine kinase (CK [CPK])	
Protein	Blood glucose	
Glucose	Cholesterol, total	
Blood	Triglyceride	
Ketone body	Urea nitrogen	
Bilirubin	Creatinine	
Urobilinogen	Uric acid	
Additional Tests:	Serum electrolytes (sodium, potassium, chloride,	
Pregnancy test (hCG test) ^a in WOCBP	calcium)	
, , , , , , , , , , , , , , , , , , , ,	PAP, TRACP-5b ^b	

^aUrine pregnancy test will be performed at screening and follow-up. If a female subject has a positive urine pregnancy test, she will undergo a serum pregnancy test according to Section 5.5 Pregnancy.

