3.7.5.2 Pharmacodynamic Assessments

3.7.5.2.1 Clinical Laboratory Tests for Pharmacodynamic Analysis (Serum Sodium Concentration, Serum Potassium Concentration, Serum Osmolality, Biomarkers, Daily Urine Sodium Excretion, Daily Urine Potassium Excretion, and Urine Osmolality)

Samples for the parameters specified in Table 3.7.5.2.1-1 will be collected according to the schedule shown in Section 3.7.1 Schedule of Assessments. The date and time of sampling of venous blood will be recorded in source documents and CRF. Serum sodium and potassium concentrations will be obtained using the data generated in clinical laboratory tests conducted at the same sampling time points discussed in Section 3.7.4.2 Clinical Laboratory Assessments. The sampling, processing, and storage procedure are provided in Appendix 1.

Table 3.7.5.2.1-1 Pharmacodynamic Laboratory Tests		
Serum: Serum sodium concentration Serum potassium concentration Serum osmolality Serum troponin-I concentration Serum NT-proBNP concentration	Plasma: Plasma AVP concentration Plasma BNP concentration Plasma Renin Activity	
Urine: Urine sodium concentration Urine potassium concentration Urine osmolality		

All samples will be sent to the contract laboratory. The contract laboratory will perform testing on all the samples according to their established procedure and report the results to the sponsor and investigator or subinvestigator. The test results reported from the contract laboratory to the sponsor in electronic format will constitute the source data. Transcription of results to the CRF is unnecessary.

To ensure subject safety and to facilitate close monitoring of serum sodium concentration by the investigator or subinvestigator, serum sodium concentration will be determined at the trial site during the treatment period separately from the measurement at the contract laboratory. Whether blood for measurement of serum sodium concentration is collected and, if collected, the date and time of blood sampling and the result of measurement will be recorded in source documents and CRF.

Daily urine sodium excretion and daily urine potassium excretion are calculated by multiplying urine sodium concentration and urine potassium concentration, respectively, by daily urine volume. Urine excretion will be calculated by the sponsor and not need to be recorded in the CRF.

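### No AST or ALT is scheduled between the Day 1 predose sample and the day after the last dose, so on scheduled tests stopping criterion 4 cannot prevent any of doses 2 to 5 for a rise that begins after dose 1

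*Protocol*

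**What the plan says.** Criterion 4 of Protocol 3.8.3.1 makes stopping mandatory when "A clinical laboratory value (AST or ALT) is obtained that equals or exceeds 3 times the upper limit of normal (ULN". AST and ALT belong to the serum chemistry panel in Table 3.7.4.2-1, which the contract laboratory tests centrally.

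The visit lists place that panel at four points:
- Screening, Day -7 to Day -4 (3.7.1.1): "serum sodium concentration, serum potassium concentration, clinical laboratory tests, physical examination, vital signs".
- Day 1, before dosing (3.7.1.4): "Clinical laboratory tests and vital signs".
- The day after the final dose, which is Day 6 for a full course (3.7.1.8).
- Follow-up, 7 to 10 days after the final dose (3.7.1.9): "Clinical laboratory tests, physical examination, and vital signs".

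On Day 2 the blood chemistry listed is "Serum sodium concentration and serum potassium concentration" (3.7.1.5). The lists for Day 3 and for Days 4 and 5 (3.7.1.6, 3.7.1.7) carry the same item. Plasma drug levels and urine tests are also listed on those days, but the clinical laboratory panel is not.

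Sodium, which drives stopping criteria 5 and 6, is followed more closely. After dose 1 it is sampled "between 4 and 6 hours after start of IMP administration, and between 8 and 12 hours after start of IMP administration" (Table 3.7-1, footnote b) and then before each later dose. In addition, "serum sodium concentration will be determined at the trial site during the treatment period separately from the measurement at the contract laboratory" (3.7.4.2).

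**The concern.** A mandatory stopping rule can protect a patient during dosing only if the value it names is measured during dosing. Under the schedule, an AST or ALT rise that starts after dose 1 would first appear on a scheduled test on Day 6, when all five doses have been given. The bilirubin check in Protocol 5.4 starts from the same AST/ALT threshold, so it too has no scheduled trigger on Days 2 to 5.

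What is at stake is up to four further doses in a patient whose transaminases are rising without symptoms, in the first trial to give OPC-61815 to heart failure patients (Protocol 1.3).

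**Working it through.** The plan gives no figure to reproduce; this is a count from the visit lists.

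**Inputs.** Five once-daily doses on Days 1 to 5 (Protocol 3.1); visit lists in 3.7.1.1 and 3.7.1.4 to 3.7.1.9; 55 subjects to be dosed (3.3.1). Central turnaround is not stated, so 1, 2 and 3 days are assumed.

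**Step 1: samples after the start of dose 1 and before dose 5.**
- Sodium/potassium: 2 on Day 1 (4 to 6 h and 8 to 12 h) + 4 predose (Days 2, 3, 4, 5) = 6.
- AST/ALT: 0.

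One sentence in 3.7.5.2.1 might seem to add the panel on Days 2 to 5: "Serum sodium and potassium concentrations will be obtained using the data generated in clinical laboratory tests conducted at the same sampling time points". It says only where the sodium and potassium data come from when time points coincide. It places no AST or ALT on a day whose list omits the panel.

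**Step 2: doses that could still be stopped.** A predose sample on Day d with a turnaround of k days is reported on Day d + k.
- Best case, result seen before that day's dose: max(0, 6 - d - k).
- Late case, result seen after that day's dose: max(0, 5 - d - k).

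| Predose sample | k = 1 (best/late) | k = 2 | k = 3 | Can show a rise after dose 1? |
|---|---|---|---|---|
| Day 1 (scheduled now) | 4/3 | 3/2 | 2/1 | No, taken before any drug |
| Day 2 (not scheduled) | 3/2 | 2/1 | 1/0 | Yes, after one dose |
| Day 3 (not scheduled) | 2/1 | 1/0 | 0/0 | Yes, after two doses |
| Day 6 (scheduled now) | 0/0 | 0/0 | 0/0 | Yes, after all doses |

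On scheduled tests, then, the doses preventable for a rise beginning after dose 1 are 0 of 4. The Day 1 row shows that criterion 4 still has a use: it can catch a patient whose values rose between the screening check (exclusion criterion 12) and dose 1.

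**Step 3: same-day site testing (k = 0, result seen after that day's dose).** Day 2: 5 - 2 - 0 = 3 doses. Day 3: 5 - 3 - 0 = 2 doses.

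**Step 4: assays for one added day.** AST, ALT and total bilirubin in 55 subjects: 3 x 55 = 165 at most.

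These counts show when a result could arrive. They do not show how often a rise would be present. A Day 2 sample helps only if the rise is already visible about 24 hours after a single dose.

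**The case against.** The strongest case against is that this is a preference about monitoring frequency.

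- **No risk basis.** Protocol 1.2 and 1.3 report no hepatic signal and no serious adverse events in phase 1. The list of frequent events in 437 tolvaptan-treated cardiac oedema patients (at least 2% and above placebo) names no hepatic event. Tolvaptan itself has been approved in Japan for this use since 2010. This stands, and it keeps the severity low.
- **Sodium is a different case.** Serum sodium rose in phase 1 and increased blood sodium is on that event list, so closer sodium sampling follows a known effect. This stands. A reader might infer from the contrast that the plan is inconsistent; it is not. The contrast shows only that a working on-treatment input is feasible.
- **Other protections exist.** Patients are hospitalised, examined and asked about adverse events daily. Criteria 3 and 10 let the investigator stop treatment, and the panel is repeated on Day 6 and at follow-up. This stands in part: a rise without symptoms may not show at examination, and criterion 4 names a laboratory value.
- **Unscheduled tests are possible.** Protocol 5.1 lets the investigator repeat or add tests to verify an abnormal result. That is optional and follows a value already seen, so it is not surveillance.
- **Stops may be unrelated to drug.** A congestion-related rise could end dosing early, and one patient is 1/11, about 9%, of an arm. This stands as a cost.

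**Conclusion.** The point holds as a low-severity, inexpensive safety improvement. Between Day 1 predose and the day after the last dose no AST or ALT is scheduled. On scheduled tests, criterion 4 therefore prevents 0 of doses 2 to 5 for a rise that begins after dose 1.

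Two stronger readings are tempting and are not supported. The first is that criterion 4 is inoperative during dosing or contradicts the schedule. It can act on a late-returning Day 1 predose value (1 to 4 doses stoppable under the assumed turnarounds) and on any unscheduled result, and no rule in the plan is broken. The second is that the schedule leaves a known liver risk unwatched. The documents report no such risk.

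The schedule finding rests on the visit lists alone and is firm. The benefit of an added sample rests on the assumed turnaround and on a rise showing within one or two doses, which the documents do not address.

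**What to change.** Amend Table 3.7-1 and either 3.7.1.5 or 3.7.1.6 so that AST, ALT and total bilirubin are run on the serum already drawn for sodium/potassium at Day 2 or Day 3 predose, with the result reviewed before later doses. Including bilirubin lets Protocol 5.4 operate from the same sample. Choose the day by the central laboratory's confirmed turnaround:
- 1 day: Day 3 (1 to 2 doses stoppable, after two doses of exposure).
- 2 days: Day 2 (1 to 2 doses, against 0 to 1 for Day 3).
- 3 days or more: central testing leaves at most 1 stoppable dose, so test at the site. In that case extend criterion 4 to name both site and central results, as criteria 5 and 6 do, and apply the upper limit of normal of the laboratory that ran the test.

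The threshold and the required action stay as they are.

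Costs:
- At most 165 assays. No extra draw is expected, but sample volume must be confirmed.
- A protocol amendment with IRB submission (Protocol 13) across about 40 sites.
- One more time point in the laboratory tables of SAP 9.3, plus CRF fields if site testing is used.
- Some Day 2 to Day 6 efficacy and pharmacodynamic data if congestion-related rises stop dosing early.

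The primary endpoint, Day 1 Cmax and AUC24h, is not put at risk, because its last sample is taken before dose 2 (Table 3.7-2).
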